## 7. CHANGES IN PLANNED ANALYSES

### 7.1. Changes from Clinical Protocol-Planned Analyses

The following changes from the protocol planned analyses are noted:

CCI

- Only treatment-emergent SAEs will be summarized. Nontreatment-emergent SAEs will be listed.
- Summary of total volume of study drug (mL) was removed from summary of exposure.

### 7.2. Changes from Previous Statistical Analysis Plans

Not applicable.

## 9. APPENDICES: Criteria of Abnormalities

**Appendix Table 1 Chemistry Laboratory Abnormalities of Interest**

Test	Unit	Predefined Change		Markedly Abnormal Criteria
		Decrease	Increase	
Fasting blood glucose a	mmol/L	3.1	3.2	NA
BUN	mmol/L	NA	NA	Value $>1.5 \times$ Baseline and $>\text{ULN}$
Creatinine	$\mu\text{mol/L}$	NA	35	Value $>$ ULN
Sodium	mmol/L	8	8	NA
Potassium	mmol/L	1.1	1.0	Value $> 5.5 \text{ mmol/L}$ or $< 3 \text{ mmol/L}$
Chloride	mmol/L	9	8	NA
Uric acid	$\mu\text{mol/L}$	NA	NA	$>1 \times \text{ULN}$
Calcium b	mmol/L	0.30	0.30	NA
AST (SGOT)	U/L	NA	NA	Value $\geq 3 \times$ Baseline Value
ALT (SGPT)	U/L	NA	NA	Value $\geq 2 \times$ Baseline Value
Gamma glutamyl transferase	U/L	NA	NA	Value $> 3 \times$ Baseline OR $>$ ULN
Alkaline phosphatase	U/L	NA	NA	Value $> 1.5 \times \text{ULN}$
Albumin c	g/dL	1	1	$<$ LLN or $>$ ULN
Total bilirubin d	$\mu\text{mol/L}$	NA	10	Value $> 1.5 \times \text{ULN}$
Lactate dehydrogenase	U/L	NA	NA	Value $\geq 2 \times$ Baseline Value
Creatine phosphokinase	U/L	NA	NA	Value $\geq 2 \times$ Baseline Value
Cystatin C	mg/L	NA	NA	$>$ ULN

aConvert to SI unit by multiplying mg/dL value by 0.0555

bmultiply mg/dL value by 0.25;

cmultiply g/dL value by 10

dmultiply mg/dL value by 17.1.

ALT = alanine aminotransferase; AST = aspartate aminotransferase; BUN = blood urea nitrogen; LLN = lower limit of normal; NA = Not Applicable; ULN = upper limit of normal

**Appendix Table 2 Hematology Laboratory Abnormalities of Interest**

Test	Unit	Markedly Abnormal Criteria
Hematocrit	1	<LLN
Hemoglobin	g/L (or mmol/L)	<LLN
Red blood cell count	trillion/L	<LLN
White blood cell count	10  /L	>1.5 × ULN or <LLN
Platelet count	10  /L	<150 or < 200 with a decrease of at least 100
Basophils (abs)	10  /L	> ULN or <LLN
Eosinophils (abs)	10  /L	> 1.5 × ULN or <LLN
Lymphocytes (abs)	10  /L	<LLN
Monocytes (abs)	10  /L	<LLN
Neutrophils (abs)	10  /L	>1.5 × ULN or <0.000001

LLN = lower limit of normal; ULN = upper limit of normal

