## 5.2. Handling of Missing Data

### 5.2.1. Imputation of Laboratory Values

Laboratory data that are continuous in nature, but are less than the lower limit of quantitation or above the upper limit of quantitation will be imputed to the value of the lower or upper limit plus or minus 2 significant digits, respectively (eg, if the results of a continuous laboratory test is < 20 or 2.0, a value of 19.99 or 1.99, respectively, will be assigned in computing summary statistics). KIM-1 values that are reported as below the level of quantitation (<0.112) will deviate from the above rule and be imputed as 0.099.

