#### **6.8.4. Clinical Laboratory Evaluation**

A shift table will present the number and percentage of patients in each cell resulting from cross-tabulating the status (low, normal, and high) of the highest/lowest post-baseline value versus that of the Baseline for each laboratory test, if applicable, by analysis period and treatment group as defined in Section 5.1. If a specific test can have both a significant low and high, then a shift table will be generated for each direction. The percentage will be based on the total number of patients in the Safety Set. A status of missing may be added, if necessary. This analysis will be repeated for last post-baseline result.

Only the highest value will be summarized for alanine aminotransferase (ALT), alkaline phosphatase, amylase, aspartate aminotransferase (AST), C-reactive protein, creatine kinase, creatinine, cystatin C, gamma glutamyl transferase (GGT), lactate dehydrogenase (LDH), total bilirubin, uric acid, absolute basophils, absolute eosinophils, basophil percent, eosinophil percent, activated partial thromboplastin time, international normalized ratio, prothrombin time, and urine KIM-1, and urine protein. Only the lowest value will be summarized for albumin, and platelets. Both the highest and lowest values will be summarized for blood urea nitrogen (BUN), calcium, chloride, glucose, potassium, sodium, absolute lymphocytes, absolute monocytes, absolute neutrophils, hematocrit, hemoglobin, lymphocyte percent, monocyte percent, neutrophils percent, white blood cell (WBC) count, and urine pH and specific gravity.

The frequency and percentage of patients meeting the potentially clinically significant abnormality criteria (defined in [Appendix Table 1](#), [Appendix Table 2](#), [Appendix Table 3](#)) at any time point post-baseline will be summarized by Analysis Period and treatment group. Additionally, the total number of potentially clinically significant abnormalities will be summarized.

Baseline value, highest/lowest value and last observation and the corresponding change from Baseline will be summarized by Analysis Period and treatment group.

All patient-level clinical laboratory values will be displayed in data listings. In addition, values meeting the potentially clinically significant abnormalities criteria will be presented in data listings. Treatment-emergent abnormalities will be indicated in the listing.

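### SAP Appendix Table 2 sets the low neutrophil limit at 0.001 cells/µL, so in practice only a reported zero can be flagged

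*SAP*

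**What the plan says.** SAP Section 9, Appendix Table 2, lists ten hematology tests with markedly abnormal criteria. The absolute neutrophil row has the unit 10^9/L and the criterion ">1.5 × ULN or <0.000001". No footnote, and no other place in either document, gives a different unit or low limit for neutrophils.

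The other rows look different. White blood cell count uses ">1.5 × ULN or <LLN". Platelets, in the same unit as neutrophils, use "<150 or < 200 with a decrease of at least 100".

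SAP 6.8.4 applies these criteria in three outputs:

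- "The frequency and percentage of patients meeting the potentially clinically significant abnormality criteria" at any post-baseline time, by analysis period and treatment group;
- the total number of such abnormalities;
- a listing, since "values meeting the potentially clinically significant abnormalities criteria will be presented in data listings".

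The incidence of hematology abnormalities is a component of the primary safety endpoint (Protocol 7.3) and of the SAP's safety endpoints (SAP 4.4.1).

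**The concern.** A low limit was written for neutrophils, but it is so close to zero that it cannot act as one. A programmer who follows the table will produce an output that shows no markedly low neutrophil count, however low the counts fall, unless a result is reported as zero. A reader could take that empty cell as a safety finding when it comes only from the threshold.

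The SAP itself treats low neutrophils as relevant: SAP 6.8.3 names leukopenia and neutropenia for additional review, and SAP 6.8.4 summarizes the lowest neutrophil value. With 8 casimersen and 4 placebo patients in the double-blind period, one patient left out changes a group percentage by 1/8 = 12.5 or 1/4 = 25 points.

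**Working it through.** **Inputs.** Limit 0.000001, unit 10^9/L (SAP Appendix Table 2). Rule for results below quantitation (SAP 5.2.1). The reporting step and quantitation limit for neutrophils are not in the documents, so ranges are assumed below.

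**1. The limit in cell counts.**
0.000001 × 10^9 cells/L = 1,000 cells/L.
1,000 cells/L ÷ 10^6 µL/L = 0.001 cells/µL.

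**2. The smallest non-zero result against the limit (assumed reporting steps).**

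| Step, 10^9/L | Cells/µL | Step ÷ 0.000001 | Below limit? |
|---|---|---|---|
| 0.1 | 100 | 100,000 | No |
| 0.01 | 10 | 10,000 | No |
| 0.001 | 1 | 1,000 | No |
| 0.000001 | 0.001 | 1 | No (equal) |

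From one to six decimals, only a reported zero is below the limit.

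**3. Could the printed unit be the slip?** No other cell-count unit printed in the table makes the number workable:

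- 10^3/L, printed for white cells: 0.000001 × 10^3 ÷ 10^6 = 10^-9 cells/µL.
- Trillion/L, printed for red cells: 0.000001 × 10^12 ÷ 10^6 = 1 cell/µL.

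**4. Could the imputation rule produce flagged values?** Under SAP 5.2.1 a result beyond a quantitation limit "will be imputed to the value of the lower or upper limit plus or minus 2 significant digits, respectively". For results of < 20 or < 2.0, "a value of 19.99 or 1.99, respectively, will be assigned in computing summary statistics". Both examples subtract 0.01: 20 − 19.99 = 0.01 and 2.0 − 1.99 = 0.01. For assumed neutrophil quantitation limits in 10^9/L:

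- 0.1 − 0.01 = 0.09, which is 90,000 times the flag limit;
- 0.05 − 0.01 = 0.04, which is 40,000 times;
- 0.02 − 0.01 = 0.01, which is 10,000 times;
- 0.01 − 0.01 = 0.00, which would be flagged.

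The exception is a quantitation limit of 0.01 or less combined with a literal subtraction of 0.01. If the rule instead scales with the limit, 0.01 becomes about 0.0099 and is not flagged.

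**5. The pattern of the table.** Low-side criteria by row:

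- `<LLN` in 8 of 10: hematocrit, hemoglobin, red cells, white cells, basophils, eosinophils, lymphocytes, monocytes;
- numeric in 2 of 10: platelets and neutrophils.

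Of the six white-cell rows, neutrophils is the only one without `<LLN`. The platelet cut reads sensibly in its printed unit; the neutrophil cut does not.

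**The case against.** The best case on the other side is that little is lost. The protocol synopsis bases laboratory abnormalities on normal ranges, and Protocol 10.3.3.4 flags any value outside the reference range. SAP 6.8.4 delivers that separately: a low/normal/high shift table with counts and percentages, using the lowest post-baseline value for a set of tests that includes "absolute lymphocytes, absolute monocytes, absolute neutrophils, hematocrit, hemoglobin". Protocol 12.4.7 presents the tables of predefined criteria as an addition for selected parameters. The safety analyses are descriptive, there are 12 patients, and every laboratory value is listed. White cell counts below LLN are flagged on their own row, and none of the laboratory stopping rules in Protocol 9.8.3 uses neutrophils.

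All of this stands, and it limits the seriousness. It does not repair the output. None of the other displays supplies the planned count of patients with a markedly low neutrophil value, and a white-cell flag can miss an isolated low neutrophil count.

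Two further points are fair. The imputation scenarios are hypothetical, and SAP 5.2.1 speaks of summary statistics, not of flagging; but the unit conversion carries the conclusion without them. A fault in reading the PDF cannot be fully excluded, although the value reads as a clean number; a look at the source settles it.

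**Conclusion.** The concern holds. As printed, the low neutrophil criterion is 0.001 cells/µL and cannot operate at any reporting step from one to six decimals unless the result is zero. The one qualification is the literal-subtraction case at a quantitation limit of 0.01 or less. The reporting step and quantitation limit are assumptions; the unit conversion is not.

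The size is modest: one side of one row of 10, affecting one table, its total and one listing. The high-side flag works, and low neutrophils remain visible elsewhere in the outputs. It should still be fixed, because the affected table reports on a component of the primary safety endpoint and would give an empty result that does not depend on the data. The documents do not show what limit was intended.

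**What to change.** Check the neutrophil cell against the source. If it is printed as quoted, the sponsor should replace the low limit with the intended one, stated correctly in 10^9/L. If no numeric cut was intended, use `<LLN` as in the other five white-cell rows. The platelet row shows that numeric cuts also occur in this table, so the sponsor must say which was meant.

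Make the change before the final outputs are programmed and while double-blind assignment is still masked; SAP 4.3.2 keeps it so until final database lock. Record it in SAP 7.2.

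At the same time, check the white cell unit, printed as 10^3/L. It alters no flag, because that row's criteria are relative to ULN and LLN, and it is not evidence of the intended neutrophil limit.

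The cost is one table cell and one unit check, with no new data or analysis. SAP 4.5.1 says periodic safety analyses have already been run; the documents do not say whether they used this table, so some re-running is possible. If `<LLN` is chosen, mild low counts will also be flagged under a heading of markedly abnormal, and more patients may appear in the table and listing.

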**Appendix Table 3 Urinalysis Laboratory Abnormalities of Interest**

Test	Markedly Abnormal Criteria
Protein in urine	> 1+

**Appendix Table 4 Vital Sign Abnormalities of Interest**

Variable	Units	Markedly Abnormal Criteria Lower limit	Markedly Abnormal Criteria Upper limit
Systolic blood pressure	mmHg	<80	>130
Diastolic blood pressure	mmHg	<40	>90
Pulse Rate	beats/minute	<50	>130
Respiratory Rate	breaths/min	<12	>20
Temperature	°C	<36.0	>38.0
Weight	kg	Decrease of 7% or more	NA

**Appendix Table 5 Electrocardiogram and Echocardiogram Abnormalities of Interest**

Variable	Units	LLN	ULN	Age Group (years)	Markedly Abnormal Criteria
Heart Rate	Beats / minute	50	120		NA
QTcF Interval	msec	NA	NA	All	Screening Visit > 450
				< 12	> 480
				≥ 12	> 500
				All	< 320 Increase > 60 >450 >480 >500
QRS Interval	msec	NA	NA	< 12	Intraventricular conduction delay (IVCD) or any QRS conduction disturbance with a QRS > 110 msec
				≥ 12	IVCD or any QRS conduction disturbance with a QRS > 120msec
PR Interval	msec	NA	NA	< 12	> 190
				≥ 12	> 220
LVEF	%	NA	NA	All	< 55%
Fractional Shortening	%	NA	NA	All	< 29%

LLN = lower limit of normal; ULN = upper limit of normal
